SAP	statistical analysis plan
SAS	statistical analysis software
SD	standard deviation
SE	standard error
SI (units)	International system of units
SOC	system organ class
SOF	sofosbuvir
SVR	sustained virologic response
SVRx	sustained virologic response x weeks after stopping study drug
TEAEs	Treatment-emergent adverse events
TFLs	tables, figures, and listings
TND	target not detected
ULN	upper limit of normal
WBC	white blood cell
WHO	World Health Organization

1. INTRODUCTION

This statistical analysis plan (SAP) describes the statistical analysis methods and data presentations to be used in tables, figures, and listings (TFLs) in the clinical study report (CSR) for Study GS-US-337-1904. This SAP is based on the protocol amendment 1.0 16 June 2017. Related documents are the original study protocol and electronic case report form (eCRF). The SAP will be finalized before database finalization. Any changes made after the finalization of the SAP will be documented in the CSR.

An interim analysis for safety was performed after a total of 11 subjects had completed Week 12 assessment or prematurely discontinued from the study before proceeding to recruitment of remaining subjects. The purpose of this interim analysis was to respond to EC committee request of safety concern on pediatric population.

1.1. Study Objectives

The primary objective of this study is as follows:

- To evaluate the efficacy of ledipasvir/sofosbuvir (LDV/SOF) in treating HCV infection in pediatric subjects who are undergoing cancer chemotherapy, as measured by the proportion who achieve a sustained virologic response 12 weeks after the end of HCV treatment (SVR12)
- To evaluate the safety and tolerability of treatment with LDV/SOF for 12 weeks

The secondary objectives of this study are as follows:

- To determine the proportion of subjects who attain SVR at 4 and 24 weeks after cessation of HCV treatment (SVR4 and SVR24)
- To evaluate the kinetics of circulating HCV RNA during treatment and after cessation of HCV treatment

The exploratory objectives of this study are:

PPD [REDACTED]

[REDACTED]

[REDACTED]

PPD

1.2. Study Design

This is a phase 2 single-center open-label study investigating the efficacy and safety of LDV/SOF FDC in pediatric subjects with chronic HCV who are receiving maintenance cancer chemotherapy.

Approximately 40 treatment naïve or experienced pediatric subjects will be enrolled in this study. Male and female children 12 to < 18 years of age, with genotype 1 or 4 HCV infection, and who are receiving a maintenance cancer chemotherapy regimen will be enrolled.

All subjects will receive LDV/SOF FDC once daily with or without food for 12 weeks. Subjects will be assigned to receive 1 LDV/SOF FDC 90 mg/ 400 mg tablet daily or 4 LDV/SOF FDC 22.5 mg/100 mg tablets once daily based on a swallowability assessment performed at screening up to Day 1.

Subjects who have indicated that they can take pills will be observed taking a placebo to match the 90 mg/ 400 mg LDV/SOF FDC tablet. If a subject is unable to swallow the 90 mg/ 400 mg LDV/SOF FDC tablet size, he/she will repeat the assessment with a placebo to match the 22.5 mg/ 100 mg LDV/SOF FDC tablet. If unable to swallow the 22.5 mg/ 100 mg LDV/SOF FDC tablet, the subject will be screen failed and excluded from the study.

The total time to complete all study visits is up to approximately 40 weeks including the following periods:

- 28-day (4-week) screening period
- 12-week treatment period
- Up to 24-week posttreatment period

The schedule of assessments is provided as an appendix to the SAP ([Appendix 1](#) **Error! Reference source not found.**).

1.3. Sample Size and Power

With approximately 40 subjects enrolled into the study, a 2-sided 95% confidence interval of the SVR12 rate will extend at most 26.6% in length, assuming the expected SVR12 rate is 80%.

The study was terminated after 19 subjects were enrolled due to extremely slow enrollment rate.

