Subjects unable to swallow the LDV/SOF FDC 90 mg/400 mg tablets and who are able to swallow LDV/SOF 22.5 mg/ 100 mg tablets (as determined by LDV/SOF FDC Swallowability Assessment at Screening or at any time up until Day 1) will be assigned to 4 LDV/SOF FDC 22.5 mg/ 100 mg tablets once daily with or without food.

Placebo tablets to match LDV/SOF FDC 90 mg/400 mg tablets and placebo tablets to match LDV/SOF 22.5 mg/ 100 mg tablets will be used for swallowability assessment.

Reference Therapy, Dose, and Mode of Administration:

None

Criteria for Evaluation:

Safety: AEs and laboratory tests will be collected throughout the study.

Efficacy: Efficacy will be evaluated using scheduled assessments of HCV RNA.

Statistical Methods:

The primary efficacy endpoint for the study is SVR12 in all enrolled and treated subjects. A point estimate with a 2-sided 95% exact confidence interval using the binomial distribution (Clopper-Pearson method) will be constructed for the SVR12 rate. No hypothesis testing will be performed.

Secondary efficacy endpoints include:

- SVR4 and SVR24
- HCV viral kinetics

Exploratory endpoints include:

PPD [REDACTED]

[REDACTED]

[REDACTED]

[REDACTED]

All continuous endpoints will be summarized using an 8-number summary (n, mean, standard deviation [SD], median, 1st quartile [Q1], 3rd quartile [Q3], minimum, maximum). All categorical endpoints will be summarized by the number and percentage of subjects who meet the endpoint definition.

Safety endpoints will be analyzed by the number and percent of subjects with events or abnormalities for categorical values or 8-number summary (n, mean, SD, median, Q1, Q3, minimum, maximum) for continuous data.

With a sample size of 40 subjects, a 2-sided 95% exact confidence interval will extend at most 26.6% in length.

This study will be conducted in accordance with the guidelines of Good Clinical Practice (GCP) including archiving of essential documents.

GLOSSARY OF ABBREVIATIONS AND DEFINITION OF TERMS

°C	degrees Celsius
°F	degrees Fahrenheit
β-hCG	β-human chorionic gonadotropin
AE	adverse event
ALT	alanine aminotransferase (also SGPT)
ANC	absolute neutrophil count
APRI	AST platelet ratio index
APTT	activated partial thromboplastin time
AST	aspartate aminotransferase (also SGOT)
AUC	area under the curve
AUC _{tau}	area under the plasma concentration versus time curve over the dosing interval (tau)
BID	twice a day
BLQ	below the lower limit of quantification
BMI	body mass index

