8.7. Sample Size

With approximately 40 subjects enrolled into the study, a 2-sided 95% confidence interval of the SVR12 rate will extend at most 26.6% in length, assuming the expected SVR12 rate is 80%.

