3.1.2. Full Analysis Set

The Full Analysis Set (FAS) includes all enrolled subjects who took at least 1 dose of study drug. The study drug in this study is LDV/SOF FDC.

This is the primary analysis set for efficacy analyses.

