3.2. Subject Grouping

This is a single arm study. All subjects received LDV/SOF 90mg/400mg daily for 12 weeks (including 90/400mg tablet or 4 22.5/100mg tablets).

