5. BASELINE CHARACTERISTICS

5.1. Demographics

Subject demographic variables (ie, age, sex, race, and ethnicity) will be summarized using descriptive statistics (n, mean, SD, median, Q1, Q3, minimum, and maximum) for age, and using the numbers and percentages of subjects for age categories (≤ 15 years old, > 15 years old), sex, race, and ethnicity. Age is calculated in years at the date of initial study drug administration. If a subject did not receive study drug after enrollment, the subject's age will be calculated from the date that the subject signed the informed consent form. The summary of demographic data will be provided for the Safety Analysis Set.

A by-subject demographic listing will be provided by subject ID number in ascending order.

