6.1.2. Primary Analysis of the Primary Efficacy Endpoint

The SVR12 rate in each of the HCV genotypes and overall will be calculated along with 2-sided 95% exact CI based on Clopper-Pearson method {20839}. No statistical hypothesis testing will be performed.

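### The 26.6% described as the greatest length of the SVR12 interval is the length at exactly 32/40, not a maximum, and SAP 1.3 gives no precision figure for the 19 subjects enrolled

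*SAP*

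**What the plan says.** SAP 1.3 ties the precision statement to approximately 40 enrolled subjects: "a 2-sided 95% confidence interval of the SVR12 rate will extend at most 26.6% in length, assuming the expected SVR12 rate is 80" per cent. Protocol 8.7 has the same condition: "will extend at most 26.6% in length, assuming the expected SVR12 rate is 80" per cent. The Statistical Methods part of the protocol synopsis drops it: "With a sample size of 40 subjects, a 2-sided 95% exact confidence interval will extend at most 26.6% in length".

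The sentence that follows in SAP 1.3 reports the early stop: "The study was terminated after 19 subjects were enrolled due to extremely slow enrollment rate". Neither that section nor any other part of the SAP gives an interval length for the smaller sample.

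The method is fixed in SAP 6.1.2, where the SVR12 rate "will be calculated along with 2-sided 95% exact CI based on Clopper-Pearson method", and Protocol 8.5.1 names the same method. Both sections rule out hypothesis testing. The denominator is the Full Analysis Set, which "includes all enrolled subjects who took at least 1 dose of study drug" (SAP 3.1.2). The SAP does not state how many of the 19 that is. SAP 3.2 says that "All subjects received LDV/SOF 90mg/400mg daily for 12 weeks", which is consistent with 19. SAP 5.1 has a rule for computing age that begins "If a subject did not receive study drug after enrollment", so it allows for an enrolled subject who was never dosed.

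**The concern.** An expected response rate does not bound the length of an exact interval. The length depends on the observed count, which varies around its expectation, and it grows as the observed proportion moves towards one half. A figure computed at exactly 80% is therefore exceeded whenever the observed rate is somewhat below 80%. The synopsis sets no condition on the rate, so its sentence has to hold for every possible result, and it does not.

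The second difficulty is that SAP 1.3 was updated to record the termination at 19 but kept the 40-subject length as its only precision figure.

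With no test, power calculation or margin in the plan, interval length is the whole quantitative case for the sample size. A study report that carries SAP 1.3 forward would repeat a bound that does not hold, beside a sample less than half the planned size.

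**Working it through.** **Inputs.** Planned n = 40 and expected rate 80% (SAP 1.3, Protocol 8.7); two-sided 95% Clopper-Pearson interval (SAP 6.1.2, Protocol 8.5.1); 19 enrolled (SAP 1.3); denominator is dosed subjects (SAP 3.1.2). True rates other than 80%, and FAS sizes of 18 and 17, are my assumptions, used to show a range.

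**Formula.** For x responders out of n, with 0 < x < n:

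- lower limit = 2.5% quantile of Beta(x, n − x + 1)
- upper limit = 97.5% quantile of Beta(x + 1, n − x)
- length = upper − lower

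The upper limit is 100% when x = n.

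**Step 1: reproduce the stated figure.** At 32/40 the interval is 64.35% to 90.95%, so the length is 26.60%. Other methods at 80% and n = 40 do not reproduce it: Wald gives 24.8%, Wald with continuity correction 27.3%, Wilson 24.3%. The origin of 26.6% is therefore clear.

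**Step 2: is it a maximum for 40 subjects?**

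| Observed | Interval | Length |
|---|---|---|
| 20/40 | 33.80% to 66.20% | 32.4% (maximum) |
| 28/40 | 53.47% to 83.44% | 30.0% |
| 30/40 | 58.80% to 87.31% | 28.5% |
| 31/40 | 61.55% to 89.16% | 27.6% |
| 32/40 | 64.35% to 90.95% | 26.6% |
| 36/40 | 76.34% to 97.21% | 20.9% |
| 40/40 | 91.19% to 100% | 8.8% |

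Every count from 9 to 31 gives an interval longer than 26.6%. If the true rate is 80%, P(X ≤ 31) for a binomial with n = 40 is 0.407, and the probability of 8 or fewer is negligible, so P(length > 26.6%) = 0.41. At a true 85% it is 0.14 and at 90% it is 0.02. The mean length at a true 80% is 26.1%, which is why 26.6% is reasonable as a planning value.

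**Step 3: the sample actually enrolled, if all 19 are in the FAS.**

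| Observed | Interval | Length |
|---|---|---|
| 9/19 or 10/19 | 24.45% to 71.14%, or 28.86% to 75.55% | 46.7% (maximum) |
| 15/19 | 54.43% to 93.95% | 39.5% |
| 16/19 | 60.42% to 96.62% | 36.2% |
| 17/19 | 66.86% to 98.70% | 31.8% |
| 18/19 | 73.97% to 99.87% | 25.9% |
| 19/19 | 82.35% to 100% | 17.6% |

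Mean length, weighting each possible result by its binomial probability:

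| True rate | n = 40 | n = 19 | Difference (points) | P(length > 26.6%), n = 19 |
|---|---|---|---|---|
| 80% | 26.1% | 37.6% | 11.5 | 0.92 |
| 90% | 20.3% | 30.0% | 9.7 | 0.58 |
| 95% | 15.7% | 24.6% | 8.9 | 0.25 |

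**Step 4: if fewer than 19 were dosed.** With 18 in the FAS, the length is 41.2% at 14/18 and 37.8% at 15/18, with a maximum of 48.0%. With 17, it is 43.1% at 13/17 and 39.6% at 14/17, with a maximum of 49.2%.

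**The case against.** The strongest reply is that 26.6% is computed correctly for the stated sample size, method and rate, and that two words are at fault. Had the condition been an observed rate of 80% or higher, the bound would be true, since the length falls steadily from 26.6% at 32/40 to 8.8% at 40/40. The 32.4% maximum needs an observed rate of 50%, far from the planning assumption, and the likely overshoot at a true 80% is a point or two. That all stands, and it is why the point concerns wording rather than calculation. It does not rescue the sentence: the text conditions on an expected rate, which leaves a 41% chance of exceeding the supposed maximum even when the assumption is true, and the synopsis has no condition at all.

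A second reply is that SAP 1.3 discloses the shortfall openly, never claims 26.6% for 19 subjects, and that readers will see the actual interval in the results. This too is fair. Projected precision matters less once enrolment is closed, and at 18/19 or 19/19 the interval would be shorter than 26.6%. Still, the section was revised to report the early stop, and the loss of precision is the direct statistical consequence of that stop. Stating it takes one clause.

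Third, nothing in the documents says that any enrolled subject went undosed; the rule in SAP 5.1 is a contingency. I agree. The 18- and 17-subject figures only show how the numbers would move.

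**Conclusion.** The concern holds. As a bound, 26.6% is false outright in the synopsis and unsupported in Protocol 8.7 and SAP 1.3; the true maximum for 40 subjects is 32.4%. For the sample obtained, the mean interval is about 9 to 11.5 percentage points longer than for 40 subjects at the same true rate, over true rates of 80% to 95%. That comparison assumes all 19 enrolled subjects are in the FAS, which SAP 3.2 supports but the SAP does not state as a count.

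The consequence is limited to the stated justification and precision of the study. No success threshold or efficacy stopping rule depends on the figure, and the exact interval will be calculated from the observed data in any case. It should be corrected because it is the only quantitative argument for the sample size and the correction is simple.

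**What to change.** First confirm the number of subjects dosed. Then replace the precision sentence in SAP 1.3, or make the correction in the CSR if the SAP is already final; SAP Section 1 provides for changes after finalization to be documented there. Suggested wording:

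*For the planned 40 subjects, the two-sided 95% exact interval would be about 26.6% long if the observed SVR12 rate were 80% (maximum 32.4%). If all 19 enrolled subjects are in the FAS, the length is about 36% to 40% near an 80% rate, 25.9% at 18/19, and at most 46.7%.*

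If fewer than 19 were dosed, recompute the second sentence for the actual FAS size; the maximum becomes 48.0% for 18 or 49.2% for 17. Add a note that this wording replaces the statement in the protocol synopsis and Protocol 8.7. The 40-subject planning rationale stays visible, correctly described.

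The cost is a short text change and a check of the dosing count. It needs no protocol amendment for this point alone, no further subjects and no change to any analysis. The stated precision becomes less favourable.

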2. TYPE OF PLANNED ANALYSIS

2.1. Data Monitoring Committee

This study does not have a data monitoring committee (DMC).

2.2. Interim Analysis

There was 1 planned interim safety analysis after 11 subjects had completed Week 12 assessment or prematurely discontinued from the study before proceeding to recruitment of remaining subjects. Decision to continue recruitment of remaining subjects was contingent on review of safety data (adverse events and laboratory abnormalities) from the first 11 subjects who completed the treatment period.

No formal interim efficacy analysis with the possibility of early termination for efficacy or futility is planned.

2.3. Final Analysis

The final analysis will be conducted when all subjects have completed the 24 week post treatment visit or prematurely discontinued from the study. The data will be finalized after all data queries are resolved for study visits through completion of the 24-week posttreatment visit. At the conclusion of data finalization, the study statistician and statistical programmers will run the final version TFLs.

3. GENERAL CONSIDERATIONS FOR DATA ANALYSES

Analysis results will be presented using descriptive statistics. For categorical variables, the number and percentage of subjects in each category will be presented; for continuous variables, the number of subjects [n], mean, standard deviation [SD] or standard error [SE], median, first quartile [Q1], third quartile [Q3], minimum, and maximum will be presented.

Data collected in the study will be presented in by-subject listings for all subjects in the Safety Analysis Set, unless otherwise specified. All by-subject listings will be presented by subject identification (ID) number in ascending order, unless otherwise specified.

3.1. Analysis Sets

Analysis sets define the subjects to be included in an analysis. Analysis sets and their definitions are provided in this section. The number of subjects eligible for each analysis set will be provided. Subjects who were excluded from each analysis set will be summarized or provided in a by-subject listing with reasons for exclusion.

3.1.1. All Enrolled Analysis Set

All Enrolled Analysis Set includes all subjects enrolled in the study after screening.

3.1.2. Full Analysis Set

The Full Analysis Set (FAS) includes all enrolled subjects who took at least 1 dose of study drug. The study drug in this study is LDV/SOF FDC.

This is the primary analysis set for efficacy analyses.

3.1.3. Safety Analysis Set

The Safety Analysis Set includes all subjects who took at least 1 dose of study drug. This is the primary analysis set for safety analyses.

3.2. Subject Grouping

This is a single arm study. All subjects received LDV/SOF 90mg/400mg daily for 12 weeks (including 90/400mg tablet or 4 22.5/100mg tablets).

3.3. Strata and Covariates

This study does not use a stratified randomization schedule for enrolling subjects.

3.4. Examination of Subject Subsets

The primary efficacy endpoint, SVR12, will be analyzed for the following subsets:

- Age group (≥ 12 - ≤ 15 years old, > 15 years old)

-
- Sex (male, female)
 - baseline weight (\leq median, $>$ median)
 - IL28B (CC, non-CC; with non-CC further broken down to CT, TT)
 - cirrhosis (presence, absence, missing)
 - HCV genotype subtypes (4a, 4b, 4c or 4d, 4h etc.)
 - baseline HCV RNA ($< 800,000$, $\geq 800,000$ IU/mL)
 - baseline alanine aminotransferase (ALT) ($\leq 1.5 \times$ upper limit of normal (ULN), $> 1.5 \times$ ULN)
 - prior HCV treatment (treatment naive, treatment experienced)
 - most recent HCV treatment response (non-responder, relapse/breakthrough, Other) for treatment-experienced subjects
 - study treatment status (completed study treatment, discontinued study treatment)
 - adherence to study regimen ($< 80\%$, $\geq 80\%$)

3.5. Missing Data and Outliers

3.5.1. Missing Data

In general, missing data will not be imputed unless methods for handling missing data are specified.

For missing last dose date of study drug, imputation rules are described in Section 3.7.1. The handling of missing or incomplete dates for AE onset is described in Section 7.1.5.2, and for prior and concomitant medications in Section 7.4.

For analyses of categorical HCV RNA data, missing posttreatment HCV RNA data will have the missing data imputed. Missing on-treatment HCV RNA will have the missing data imputed up to the time of the last dose (for on-treatment displays). If the study day associated with the last dosing date is greater than or equal to the lower bound of a visit window, and the value at the visit is missing, the value will be imputed. If the study day associated with the last dosing date is less than the lower bound of a visit window then the on-treatment value at that visit will remain missing.

If a data point is missing and is preceded and followed in time by values that are “< LLOQ target not detected (TND)”, then the missing data point will be set to “< LLOQ TND”. If a data point is missing and preceded and followed by values that are “< LLOQ detected”, or preceded by “< LLOQ detected” and followed by “< LLOQ TND”, or preceded by “< LLOQ TND” and followed by “< LLOQ detected”, then the missing value will be set to “<

LLOQ detected”. In these situations the data point will be termed a bracketed success; otherwise, the data point will be termed a bracketed failure (ie, \geq LLOQ detected). If a data point is missing and is not bracketed, the missing data point will also be termed a failure (ie, \geq LLOQ detected) except for SVR24, which will be imputed according to SVR12 status. Success for SVR12 who have no further HCV RNA measurements collected will be counted as a success for SVR24 due to the high correlation between these 2 endpoints.

For the analyses of continuous HCV RNA efficacy data, when and only when a missing HCV RNA value is imputed as $<$ LLOQ TND or $<$ LLOQ detected according to the imputation rule described above, the corresponding continuous value will be imputed to LLOQ - 1 IU/mL. No other imputation will be performed for continuous HCV RNA data.

3.5.2. Outliers

Outliers will be identified during the data management and data analysis process, but no sensitivity analyses will be conducted. All data will be included in the data analysis.

3.6. Data Handling Conventions and Transformations

By-subject listings will be presented for all subjects in the Safety Analysis Set sorted by subject ID number, visit date, and time (if applicable) unless otherwise specified. Data collected on log forms, such as AEs, will be presented in chronological order within subject.

Age (in years) on the date of the first dose of study drug will be used for analyses and presentation in listings.

If a subject was not dosed with study drug at all, then the date the informed consent was signed will be used instead of the first dose date of study drug.

Data that are continuous in nature but are less than the lower limit of quantitation or above the upper limit of quantitation will be imputed as follows:

- A value that is one unit less than the limit of quantitation will be used for calculation of descriptive statistics if the datum is reported in the form of “ $< x$ ” (where x is considered the limit of quantitation). For example, if the values are reported as < 50 and < 5.0 , values of 49 and 4.9, respectively, will be used for calculation of summary statistics. An exception for this rule is any value reported < 1 . For the values reported as < 1 or < 0.1 , value of 0.9 or 0.09 will be used for calculation of summary statistics.
- A value that is one unit above the limit of quantitation will be used for calculation of descriptive statistics if the datum is reported in the form of “ $> x$ ” (where x is considered the limit of quantitation). Values with decimal points will follow the same logic as above.
- The limit of quantitation will be used for calculation of descriptive statistics if the datum is reported in the form of “ $\leq x$ ” or “ $\geq x$ ” (where x is considered the limit of quantitation).

The artus® HCV RG RT-PCR Kit by QIAGEN March 2015 was used to determine HCV RNA results in this study. The lower limit of quantitation (LLOQ) of this assay is 50 IU/mL.

When the calculated IU/mL is within the linear range of the assay, then the result will be reported as the “<< numeric value>> IU/mL”. This result will be referred to in this document as the numeric result or as “≥ LLOQ detected” for categorical result.

When HCV RNA is not detected, the result is reported as “HCV RNA not detected” or “target not detected”. This result will be referred to in this document as “< LLOQ target not detected” or “< LLOQ TND”.

When the HCV RNA IU/mL is less than LLOQ of the assay, the result is reported as “<50 IU/mL HCV RNA detected”. This result will be referred to in this document as “< LLOQ detected”.

The overall category of HCV RNA < LLOQ includes “< LLOQ TND” and “< LLOQ detected.”

For numerical HCV RNA data, values below LLOQ will be set to the LLOQ – 1 IU/mL. (ie, 49 HCV RNA IU/mL). HCV RNA values returned as “No HCV RNA detected” will also be set to 49 IU/mL.

For selected analyses, HCV RNA data (IU/mL) will be transformed to the logarithmic (base 10) scale (\log_{10} IU/mL).

